- An additional 3 samples will be collected in the first 9 subjects in each age stratum, if the dose being evaluated in Part C was not evaluated in Part B (i.e. a total of 6 samples will be collected in these 9 subjects). These samples will be taken 4-5 h and 12 h Post-Dose 1 and Pre-Dose 7 (or pre-Dose 8 if the Dose 6 sampling was conducted relative to Dose 7). The DSMC will review the PK data profiles and recommend whether these PK samples are to be taken for subjects enrolled subsequently. Please refer to [Table 5](#) for PK sample schedule.
- The actual day for taking each PK sample is dependent on the time when IMP is administered on Visit 1 (Day 1) (morning versus afternoon versus evening); eg, if the subject received their first dose of IMP at 22:00 on Day 1, the post-dose samples due to be taken at 4-5 h, and 12 h would be taken on Day 2 from 02:00 to 03:00, and 10:00 respectively
- ^t The timing of the Post-Dose PK samples and assessments in Part C will be 4-5 h Post-Dose.
- ^u If the subject is discharged from the hospital and the timing of the Dosing Visit 3 assessments Pre-Dose 6 and Post-Dose 6 fall at a time when it is not appropriate for the subject to return to the hospital or accept a home visit, the Pre-Dose 6 and Post-Dose 6 assessments can be moved relative to Dose 7.
- ^v If the PK sampling at Dose 6 is moved relative to Dose 7, then the Pre-Dose 7 PK sample will be moved to Pre-Dose 8. (Note: If the PK sampling is taken relative to Dose 6 then the PK sample should be taken Pre-Dose 7.)
- ^w If the subject is discharged from hospital, a nasopharyngeal swab sample should be obtained prior to discharge. Note: this sample is not required if the previous sample was taken less than 12 hours before the subject is discharged. See Table 4 for nasopharyngeal swab sample schedule. Samples taken post-discharge at Dosing Visits 3, 4 and 5 are to be spaced evenly such that the nasopharyngeal swab samples are taken daily at a similar time each day. For instance, the samples should either be taken Pre-Dose 5, Pre-Dose 7 and Pre-Dose 9, OR Pre-Dose 6, Pre-Dose 8 and Pre-Dose 10.
- ^x After discharge the assessment for concomitant medication and Adverse events should be conducted daily during the outpatient visit, whilst the parent/caregiver will record in the Patient Booklet their assessment for doses given at home.
- ^y IMP should be administered every 12 hours or as dosing regimen recommended by the Data Safety Monitoring Committee with a time window of ± 30 minutes. The times of the prior feeding and first feeding after dosing should be recorded.
- () Denote samples and assessments that can be taken on either Dosing Visit

Table 4. Nasopharyngeal Sampling Schedule for the Study

Part	Dosing Visit 1				Dosing Visit 2	Dosing Visit 3	Dosing Visit 4	Dosing Visit 5	Visit Day 7	Visit Day 14	Visit Day 34	
A	-2 h to 0 h Pre-Dose (1 sample)	12 h Post- Dose 1 ^{bc} (optional)	1 sample collected 24 h Post-Dose ^b	1 sample collected at 36 h Post-Dose ^{bc} (optional)	1 sample at 48 h Post-Dose 1 ^b	NA	NA	NA	NA	NA	NA	NA
B	-2 h to 0 h Pre-Dose (1 sample)	12 h Post- Dose 1 (Pre-Dose 2) ^{bc} (optional)	NA	NA	1 sample collected Pre-Dose 3 ^b . Pre-Dose 4 ^c sample (optional) Up to 2 samples in total ^b	1 sample collected prior to each dose; Up to 2 samples in total ^{ab}	1 sample collected Pre-Dose 7 ^b . Pre-Dose 8 ^c sample (optional) Up to 2 samples in total* ^b	1 sample collected Pre-Dose 9 ^b Pre-Dose 10 ^c sample (optional). Up to 2 samples in total* ^b	+40-48 h Post-Dose 10	NA	NA	NA
C	-2 h to 0 h pre-dose (1 sample)	12 h Post Dose 1 (pre-dose 2) ^{bc} (optional)	NA	NA	1 sample collected prior to each dose. Pre-Dose 4 ^c sample (optional). Up to 2 samples in total ^b	1 sample collected prior to each dose; Up to 2 samples in total ^{ab}	1 sample collected Pre-Dose 7 ^b . Pre-Dose 8 ^c sample (optional). Up to 2 samples in total* ^b	1 sample collected Pre-Dose 9 ^b . Pre-Dose 10 ^c sample (optional). Up to 2 samples in total* ^b	+40-48h Post Dose 10	1 Sample	1 Sample	1 Sample
Part C subjects discharged prior to Dosing Visit 3:												
C	-2 h to 0 h pre-dose (1 sample)	12 h Post Dose 1 (pre-dose 2) ^{bc} (optional)	NA	NA	1 sample ^{a,b} collected prior to either Dose 3 or 4.	1 sample ^{b,d,e} collected prior to either Dose 5 or 6	1 sample ^{b,c} collected prior to either Dose 7 or 8	1 sample ^{b,c} collected prior to either Dose 9 or 10	+40-48h Post Dose 10 (1 sample)	1 Sample	1 Sample	1 Sample

Footnotes appear on next page.

Abbreviations: h = hours; IMP = investigational medicinal product; NA = not applicable

Notes:

All procedures and assessments are presented against the Dosing Visit at which they should be conducted. The actual day(s) on which the visit falls is dependent upon the time that investigational medicinal product (IMP) is administered during Dosing Visit 1. The Follow-up +40-48 h Post-Dose 10 on Visit Day 7 could therefore occur on Study Day 7 or 8, depending on when the subject received his or her first dose of IMP.

CCI

^a If the subject is discharged from hospital, a nasopharyngeal swab sample should be obtained prior to discharge. Note: This sample is not required if the previous sample was taken less than 12 hours before the subject is discharged.

^b Nasopharyngeal swab sampling window is 60 minutes.

^c Pre-dose 2, 4, 8 and 10 are optional nasopharyngeal swab samples in study Part B.

^d If the subject is discharged prior to completion of Dosing Visit 3 it may be necessary to move the Pre-Dose 6 nasopharyngeal swab sample relative to Dose 7

^e Samples taken post-discharge at Dosing Visits 2, 3, 4 and 5 are to be spaced evenly such that the nasopharyngeal swab samples are taken daily at a similar time each day. For instance, the samples should either be taken Pre-Dose 3, Pre-Dose 5, Pre-Dose 7 and Pre-Dose 9, OR Pre-Dose 4, Pre-Dose 6, Pre-Dose 8 and Pre-Dose 10.

* Procedure to be done if subject is in the hospital.

Table 5. PK Sampling Schedule for the Study

Part	Treatment Phase					Post Treatment Phase	Total Number of Samples
	Dosing Visit 1	Dosing Visit 2	Dosing Visit 3	Dosing Visit 4	Dosing Visit 5	Visit Day 7	NA
A: Single Dose	1-2 h, 4-5 h, 6-8 h, 12 h ^a , 18-24 h	NA	NA	NA	NA	NA	5
B*: Multiple Dose	1-2 h or 4-5 h or 6-8 h Post-Dose 1, 12 h ^a Post-Dose 1 (Pre-Dose 2)	NA	Pre-Dose 6, 1-2 h or 4-5 h or 6-8 h Post-Dose 6.	12 h ^a Post-Dose 6 (Pre-Dose 7)	NA	40-48 h Post-Dose 10	6
C**: Multiple Dose	4-5 h Post-Dose 1 ^c , 12 h ^a Post-Dose 1 (Pre-Dose 2)	NA	Pre-Dose 6 ^{bc} 4-5 h Post-Dose 6 ^{bc}	12 h ^a Post-Dose 6 (Pre-Dose 7)	NA	40-48 h Post-Dose 10 ^b	3 or 6 ^b
Part C subjects discharged prior to Dosing Visit 3:							
C**: Multiple Dose	4-5 h Post-Dose 1 ^c , 12 h ^a Post-Dose 1 (Pre-Dose 2)	NA	(Pre-Dose 6 ^{b,c,d}) (4-5 h Post-Dose 6 ^{b,c,d}) (12 h ^{a,d} Post-Dose 6/Pre-Dose 7) OR (Pre-Dose 7 ^{b,c,d}) (4-5 h Post-Dose 7 ^{b,c,d}) (12 h ^{a,d} Post-Dose 7/Pre-Dose 8)	NA	NA	40-48 h Post-Dose 10 ^b	3 or 6 ^b

Footnotes appear on next page.

Abbreviations: h = hours; IMP = investigational medicinal product; NA = not applicable; PK = pharmacokinetic.

Notes: All procedures and assessments are presented against the Dosing Visit at which they should be conducted. The actual day(s) on which the visit falls is dependent upon the time that investigational medicinal product (IMP) is administered during Dosing Visit 1. The Follow-up +40-48 h Post-Dose 10 on Visit Day 7 could therefore occur on Study Day 7 or 8, depending on when the subject received his or her first dose of IMP.

* For PK Part B: After the review of PK analysis from Part A, it will be decided if the PK sample after the First Dose will be taken 1-2 h, 4-5 h Post Dose 1 or 6-8 h Post-Dose 1. The same time point will be taken on Dosing Visit 3 (either 1-2 h, 4-5 h or 6-8 h Post-Dose 6). Based on the Part A PK analysis, it will be decided if the Samples planned relative to Dose 6 should stay as planned or shifted relative to Dose 10 with the same time structure. In case the PK samples are shifted relative to Dose 10, then an additional PK sample 18-24 h Post-Dose 10 will be taken.

** For PK Part C: The same PK time point Post-Dose 6 will be taken as in Part B, at 4-5 h Post-Dose 6.

^a The 12-hour PK sampling window is 30 minutes.

^b If the PK profile for a dose to be evaluated in Part C *was evaluated* in Part B, only 3 PK samples will be drawn: Pre-Dose 6, 4-5 h Post Dose 6 sample and Visit Day 7. If the PK profile *was not evaluated* in Part B, a total of six PK samples will be drawn as detailed in the table above.

^c The timing of the Post-Dose PK samples and assessments in Part C will be 4-5 h Post-Dose.

^d If the subject is discharged after completion of Dosing Visit 1 it may be necessary to move the Pre-Dose 6 and 4-5 h Post-Dose 6 PK sampling relative to Dose 7. If the PK Tmax sampling is moved relative to Dose 7 then the Pre-Dose 7 PK sample will be moved to Pre-Dose 8

() Denote samples and assessments that can be taken on either Dosing Visit

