Abbreviations: ECG = electrocardiogram; h = hours; PK = pharmacokinetic; RSV = respiratory syncytial virus; TFU = Telephone Follow-up Visit.

Notes: All procedures and assessments are presented against the Dosing Visit at which they should be conducted. The actual day(s) on which the visit falls is dependent upon the time that investigational medicinal product (IMP) is administered during Dosing Visit 1. The Follow-up +40-48 h Post-Dose 10 on Visit Day 7 could therefore occur on Study Days 7 or 8, depending on when the subject received his or her first dose of IMP. Observations (SpO₂, viral signs, inspection of RSV symptoms) should precede any procedures that manipulate the subject (physical examination, nasopharyngeal swabs, PK sampling). For the physical examination, listen to the lungs first. In any event, the order should be consistent for all the assessment days.

- ^a Written informed consent includes the consent for participating in Part B of the study and the written informed consent for the optional Sponsor-provided commercial RSV test.
- ^b Demographic data to be collected: date of birth, gender, race, and ethnicity.
- ^c Physical examination may also include a symptom-directed examination, general condition, lung auscultation, and respiratory muscles retractions (Section 10.1.3.8). For days when IMP is administered, physical examination should be conducted before a dose of IMP is administered.
- ^d Refer to Appendix 17.5 for the Dehydration Status Evaluation.
- ^e Vital signs include body temperature, systolic and diastolic blood pressure, respiratory rate, heart rate and should be conducted before PK and nasopharyngeal swab samples, for the respective time points, are taken. For the days without PK and nasopharyngeal swab samples, vital signs should be taken before a dose of IMP is administered.
- ^f 12-Lead ECG to be performed using the centrally provided ECG machine and before PK and nasopharyngeal swab samples are taken. For days when IMP is administered ECG should be performed before a dose of IMP is administered
- ^g Refer to Appendix 17.1 for the RSV Clinical Scoring System. Note: this assessment is to be done only when subject is hospitalised and at follow-up.
- ^h Refer to Appendix 17.4 for RSV signs and Symptoms
- ⁱ Refer to Appendix 17.2 for the Adapted version of ReSVinet scale for parental use.

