- ^e Physical examination may also include a symptom-directed examination, general condition, lung auscultation, and respiratory muscles retractions (Section 10.1.3.8). For days when IMP is administered, physical examination should be conducted before a dose of IMP is administered.
- ^f Refer to Appendix 17.5 for the Dehydration Status Evaluation.
- ^g Hydration status post-discharge is to be taken daily at a similar time each day.
- ^h Vital signs include body temperature, systolic and diastolic blood pressure, respiratory rate, heart rate and should be conducted before PK and nasopharyngeal swab samples, for the respective time points, are taken. For the days without PK and nasopharyngeal swab samples, vital signs should be taken before a dose of IMP is administered.
- ⁱ Vital signs post-discharge are to be taken daily at a similar time each day and must be taken prior to PK and nasopharyngeal swab sampling
- ^j 12-Lead ECG to be performed using the centrally provided ECG machine and before PK and nasopharyngeal swab samples are taken. For days when IMP is administered ECG should be performed before a dose of IMP is administered unless a post-dose ECG is scheduled.
- ^k Only one ECG is required at either Dosing Visit 3 or Dosing Visit 4. This ECG should be taken either 4-5 h Post-Dose 6 or 4-5 h Post-Dose 7 to coincide with the PK sampling. ECG should be performed prior to the PK sample being collected.
- ^l Refer to Appendix 17.6 for the ReSVinet score for clinicians.
- ^m ReSVinet score post-discharge are to be taken daily at a similar time each day.
- ⁿ Refer to Appendix 17.4 for RSV Signs and Symptoms
- ^o RSV Signs and Symptoms post-discharge are to be taken daily at a similar time each day.
- ^p Refer to Appendix 17.2 for the Adapted version of ReSVinet scale for parental use. Upon discharge parents/caregivers are to complete at a similar time each day at home.
- ^q At Screening, the AST/ALT values should be obtained from the local laboratory. A Screening blood sample will also need to be sent to the Central laboratory.
- ^r Allowed time window on the end of treatment safety bloods and urinalysis is +/- 2 days.

- ^s PK samples to be collected Pre-Dose 6 and 4-5 h Post-Dose 6 and 40-48 h Post Dose 10 (Visit Day 7) in all subjects (3 samples). If the Pre- and post-Dose 6 sampling times are at a time that is unsuitable for the subject to return to the clinic or accept a home visit, then these can be taken Pre-Dose 7 and 4-5 h Post-Dose 7 instead.

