9.3 Treatment Period Part B

9.3.1 Dosing Visit 1 (Part B)

-2 Hours to 0 Hours Pre-Dose 1:

- Reassess for eligibility against the inclusion and exclusion criteria
- Physical examination (symptom-directed examination, general condition, lung auscultation, and respiratory muscles retractions)
- Evaluation of hydration status
- Vital signs (body temperature, systolic and diastolic BP, HR, RR)
- Record the use of supplemental oxygen, method of delivery (eg, nasal cannula), percent O₂/flow rate supplied
- Pulse oximetry on room air (if deemed safe by PI or health care provider)
- RSV Clinical Scoring System ([Appendix 17.1](#))
- Record RSV-related signs and symptoms and severity every 12 hours (if indicated), including: temperature, cough, coryza, grunting with expiration, nasal flaring, retractions, and wheezing.
- Nasopharyngeal swab according to sampling schedule in Table 4
- Concomitant medication review
- Adverse event review
- Randomisation for eligible subjects

Note: If any of the assessments above were carried out within 2h Pre-Dose 1 for screening purposes, it is not necessary to repeat that assessment for the -2h to 0h Pre-Dose 1 timepoint. However, if the assessment was carried out >2 h prior to Dose 1 for screening purposes (i.e. within the first 22 hours of the screening window), the assessment must be repeated between -2h to 0h Pre-Dose 1.

Dosing (0 Hours):

- Vital signs (body temperature, systolic and diastolic BP, HR, RR)
- Study medication administration
- The times of the prior feeding and first feeding after dosing should be recorded.
- Adverse event review
- Concomitant medication review

1-2 Hours or 4-5 Hours or 6-8 Hours Post-Dose 1:

The following assessments will be carried out at either 1 to 2 hours, 4 to 5 hours or 6 to 8 hours Post-Dose 1. The time point chosen (1-2, 4-5 or 6-8 hours) will be defined after PK analysis of Part A.

- Vital signs (body temperature, systolic and diastolic BP, HR, RR)
- 12-Lead ECG
- PK blood sample according to sampling schedule in [Table 5](#)
- Concomitant medication review
- Adverse event review

12 Hours Post-Dose 1 (Pre-Dose 2):

- Vital signs (body temperature, systolic and diastolic BP, HR, RR)
- Pulse oximetry on room air (if deemed safe by PI or health care provider)
- Record the use of supplemental oxygen, method of delivery (eg, nasal cannula), percent O₂/flow rate supplied

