9.3.3 Dosing Visit 3 (Part B)

Dose 5:

Pre-Dose 5:

- Evaluation of hydration status
- Vital signs (body temperature, systolic and diastolic BP, HR, RR)
- 12-Lead ECG
- Record the use of supplemental oxygen, method of delivery (eg, nasal cannula), percent O₂/flow rate supplied
- Pulse oximetry on room air (if deemed safe by PI or health care provider)
- Record RSV-related signs and symptoms, and severity every 12 hours (if subject remains hospitalised), including: temperature, cough, coryza, grunting with expiration, nasal flaring, retractions, and wheezing
- RSV Clinical Scoring System performed every 24 hours ([Appendix 17.1](#))
- Nasopharyngeal swab according to sampling schedule in Table 4
- Concomitant medication review
- Adverse event review
- Study medication administration (Dose 5)
- The times of the prior feeding and first feeding after dosing should be recorded.

Dose 6:

Pre-Dose to 0 Hours:

- Vital signs (body temperature, systolic and diastolic BP, HR, RR)
- Record the use of supplemental oxygen, method of delivery (eg, nasal cannula), percent O₂/flow rate supplied
- Pulse oximetry on room air (if deemed safe by PI or health care provider)
- Record RSV-related signs and symptoms, and severity every 12 hours (if indicated), including: temperature, cough, coryza, grunting with expiration, nasal flaring, retractions, and wheezing
- PK blood sample according to sampling schedule in [Table 5](#)
- Nasopharyngeal swab according to the sampling schedule in Table 4
- Concomitant medication review
- Adverse event review
- Study Medication administration (Dose 6)
 - The times of the prior feeding and first feeding after dosing should be recorded.

1-2 Hours OR 4-5 Hours OR 6-8 Hours Post-Dose 6:

The following assessments will be carried out at either 1 to 2 hours, 4 to 5 hours or 6 to 8 hours Post-Dose 6. The time point chosen (1-2, 4-5 or 6-8 hours) will be defined after PK

analysis of Part A and sites will be notified of the chosen time point in the Dosing Guidance letter.

- Vital signs (body temperature, systolic and diastolic BP, HR, RR)
- 12-Lead ECG
- PK blood sample according to sampling schedule in [Table 5](#)
- Concomitant medication review
- Adverse event review

If a subject is discharged:

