9.4.1 Dosing Visit 1 (Part C)

-2 Hours to 0 Hours Pre-Dose 1:

- Reassess for eligibility against the inclusion and exclusion criteria
- Physical examination
- Evaluation of hydration status
- Vital signs (body temperature, systolic and diastolic BP, HR, RR)
- ReSVinet Scale for Clinicians ([Appendix 17.6](#))
- Record RSV-related signs and symptoms, and severity every 12 hours (if indicated), including: temperature, cough, coryza, grunting with expiration, nasal flaring, retractions, and wheezing

- Record the use of supplemental oxygen, method of delivery (eg, nasal cannula), Percent O₂/Flow rate supplied
- Pulse oximetry on room air (if deemed safe by PI or health care provider)
- Randomisation for Eligible Subjects (stratified by age group)
- Nasopharyngeal swab
- Concomitant medication review
- Adverse Events

Note: If any of the assessments above were carried out within 2 h Pre-Dose 1 for screening purposes, it is not necessary to repeat that assessment for the -2 h to 0 h Pre-Dose 1 timepoint. However, if the assessment was carried out >2 h prior to Dose 1 for screening purposes (i.e. within the first 22 hours of the screening window), the assessment must be repeated between -2 h to 0 h Pre-Dose 1.

Dosing (0 Hours):

- Concomitant medication review
- Adverse event review
- Study medication administration (Dose 1)
 - The times of the prior feeding and first feeding after dosing should be recorded.

+4-5 Hours Post-Dose 1:

The following assessments will be carried out at 4 to 5 hours Post-Dose 1.

- Vital signs (body temperature, systolic and diastolic BP, HR, RR)
- 12-Lead ECG
- Concomitant medication review
- Adverse event review
- PK blood sample according to sampling schedule in [Table 5](#). **Note:** This sample will only be required if the dose level was not previously evaluated in Part B.

12 Hours Post-Dose 1 (Pre-Dose 2):

- Vital signs (body temperature, systolic and diastolic BP, HR, RR)
- Record RSV-related signs and symptoms, and severity every 12 hours (if indicated), including: temperature, cough, coryza, grunting with expiration, nasal flaring, retractions, and wheezing
- Record the use of supplemental oxygen, method of delivery (eg, nasal cannula), Percent O₂/Flow rate supplied
- Pulse oximetry on room air (if deemed safe by PI or health care provider)
- Optional Nasopharyngeal swab according to sampling schedule in [Table 4](#)
- Concomitant medication review
- Adverse event review

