9.4.3 Dosing Visit 3 (Part C)

Procedures and assessments scheduled for Dosing Visit 3 in Part C are required if the subject is currently hospitalised. If the subject has met the criteria for early discharge and is being seen as an outpatient the required assessments are listed in [Section 9.4](#) and [Table 3b](#). In case of early discharge, provide parent with Patient Booklet, video access link and clear instructions how to administer IMP. An additional nasopharyngeal swab sample should be taken according to Table 4 if the last nasopharyngeal swab sample was taken > 12 hours prior to discharge.

Pre-Dose 5 (All of the assessments to be completed if still an in-patient):

- Evaluation of hydration status
- Vital signs (body temperature, systolic and diastolic BP, HR, RR)
- 12-Lead ECG
- ReSVinet scale for clinicians ([Appendix 17.6](#))
- Adapted ReSVinet scale for parental use ([Appendix 17.2](#))
- Record RSV-related signs and symptoms, and severity every 12 hours (if indicated), including: temperature, cough, coryza, grunting with expiration, nasal flaring, retractions, and wheezing
- Record the use of supplemental oxygen, method of delivery (eg, nasal cannula), Percent O₂/Flow rate supplied
- Pulse oximetry on room air (if deemed safe by PI or health care provider)
- Nasopharyngeal swab according to sampling schedule in Table 4
- Concomitant medication review
- Adverse event review
- Study Medication Administration (Dose 5)
 - The times of the prior feeding and first feeding after dosing should be recorded.

Dose 6 (All of the assessments to be completed if still an in-patient)

Pre-Dose to 0 Hour:

- Vital signs (body temperature, systolic and diastolic BP, HR, RR)
- Record RSV-related signs and symptoms, and severity every 12 hours (if indicated), including: temperature, cough, coryza, grunting with expiration, nasal flaring, retractions, and wheezing
- Record the use of supplemental oxygen, method of delivery (eg, nasal cannula), Percent O₂/Flow rate supplied
- Pulse oximetry on room air (if deemed safe by PI or health care provider)
- PK blood sample according to sampling schedule in [Table 5](#)
- Nasopharyngeal swab according to sampling schedule in Table 4
- Concomitant medication review
- Adverse event review
- Study Medication Administration (Dose 6)
 - The times of the prior feeding and first feeding after dosing should be recorded.

+4-5 Hour Post-Dose 6:

The following assessments will be carried out at 4 to 5 hours Post-Dose 6.

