10.1.3.9 Electrocardiograms

A 12-lead ECG will be performed at Screening. Additional 12 lead ECGs will be performed at scheduled time points as indicated in the relevant Schedule of Assessments for Part A (Table 1), Part B (Table 2), and Part C (Table 3a inpatients and Table 3b outpatients) in Section 8.1.

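### Footnote f of Protocol Tables 2 and 3a puts every dosing-day ECG before a dose, but the same row and the visit sections put the Dose 1 and Dose 6 ECGs after it

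*Protocol*

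**What the plan says.** Footnote f is attached to the 12-lead ECG row of Protocol Table 2 and of Table 3a (Section 8.1). After asking for the central machine and for the ECG to precede PK and swab sampling, it says in both tables: "For days when IMP is administered ECG should be performed before a dose of IMP is administered". No exception follows.

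Table 3b, for Part C infants discharged before Dosing Visit 3, has the corresponding rule as footnote j, with an exception added: "For days when IMP is administered ECG should be performed before a dose of IMP is administered unless a post-dose ECG is scheduled".

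The visit sections time the Dose 1 and Dose 6 ECGs after the dose:

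- Part B, Section 9.3.1: "The following assessments will be carried out at either 1 to 2 hours, 4 to 5 hours or 6 to 8 hours Post-Dose 1". The list that follows includes the ECG.
- Part B, Section 9.3.3: "The following assessments will be carried out at either 1 to 2 hours, 4 to 5 hours or 6 to 8 hours Post-Dose 6". The list again includes the ECG, and "sites will be notified of the chosen time point in the Dosing Guidance letter".
- Part C, Section 9.4.1: "The following assessments will be carried out at 4 to 5 hours Post-Dose 1". The list includes the ECG.
- Part C, Section 9.4.3: "The following assessments will be carried out at 4 to 5 hours Post-Dose 6". The list includes the ECG.

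Section 10.1.3.9 sends the reader back to the tables: "Additional 12 lead ECGs will be performed at scheduled time points as indicated in the relevant Schedule of Assessments".

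**The concern.** The row and its own footnote give different instructions for two ECGs. The footnote also gives site staff no warning of this: an ECG done before the dose is also before the PK sample, so it satisfies everything footnote f asks.

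Those two ECGs are the only ones in the dosing period planned within hours of a dose. The others come just before Doses 3, 5, 8 and 10, at the end of the planned 12-hour interval, and the Day 7 ECG is 40-48 hours after Dose 10. In Part B the two post-dose ECGs sit in the same block as the post-dose PK sample, and Section 7.1.1 names ECG change from baseline at predefined time points as a primary safety endpoint. An ECG taken at the wrong time cannot be repeated later.

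In Part C, ECG is not among the endpoints listed in Section 7.2, so less depends on it there. The post-dose ECG is still clearly wanted: for infants seen as outpatients, Section 8.2 asks that visits be arranged so that it is done at steady state.

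**Working it through.** There is no sample-size or error-rate figure to reproduce. The check sets the footnote against the row and the visit text, ECG by ECG.

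| Dosing-day ECG | Mark in Tables 2 and 3a | Visit text, Part B / Part C | Agrees with footnote f? |
|---|---|---|---|
| Dose 1 | Post-dose column only | 9.3.1 / 9.4.1: after the dose | No |
| Dose 3 | Dose 3 | 9.3.2 / 9.4.2: before | Yes |
| Dose 5 | Dose 5 | 9.3.3 / 9.4.3: before | Yes |
| Dose 6 | Post-dose column only | 9.3.3 / 9.4.3: after the dose | No |
| Dose 8 (if in hospital) | Dose 8 | 9.3.4 / 9.4.4: before | Yes |
| Dose 10 (if in hospital) | Dose 10 | 9.3.4 / 9.4.4: before | Yes |

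In both tables the ECG row is blank in the pre-Dose 1 column and at 0 h for Doses 1 and 6. No ECG is listed in the pre-Dose 1 or pre-Dose 6 blocks of the visit sections.

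**Counts**

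- Infant in hospital for all doses: 6 dosing-day ECGs, 2 of them post-dose (2/6).
- Infant discharged after Dosing Visit 3: the ECGs before Doses 8 and 10 drop out, leaving 6 − 2 = 4, of which 2 are post-dose (2/4).
- Worst case, if a site moves both ECGs to before the dose: 0/6 or 0/4 post-dose.

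**Can the footnote be read so that it agrees with the row?** One could say that an ECG after Dose 1 is also before Dose 2. On that reading every ECG between doses complies, and the exception in Table 3b footnote j would have nothing to except. Footnotes c and e of the same tables also use the before-a-dose phrase as an ordinary pre-dose instruction.

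**Comparison across tables.** Part A also has a post-dose ECG (4-5 h), but Table 1 footnote h contains no before-dose rule. Table 3b has post-dose ECGs and the rule with its exception. Only Tables 2 and 3a combine post-dose ECGs with an unqualified rule.

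**The case against.** The strongest reply is that footnote f is a rule for days, not for individual ECGs. Dosing Visit 3 already has an ECG before Dose 5, which meets the rule, so the post-Dose 6 ECG is simply an additional one. On this view only Dose 1 conflicts, and the worst case of no post-dose ECG is not forced. Table 3b would need its exception because it has no pre-Dose 5 ECG and merges Doses 5 and 6 into one column without hours.

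This reading concedes Dose 1, and it does not clear Dose 6. Footnote f is attached to the whole row, so it governs each ECG in it. Nor does a dosing visit always fall within one calendar day. In the tables' own example of a first dose at 22:00 on Day 1, with doses every 12 hours, Dose 5 falls at 22:00 on Day 3 and Dose 6 at 10:00 on Day 4. The only ECG scheduled on Day 4 is then the one after Dose 6, with no pre-dose ECG that day to satisfy a per-day rule. The layout argument does not reach Dose 1 either, because Table 3b has the same separate 4-5 h column there as Table 3a.

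The rest of the reply is about consequence, and much of it stands. The column headers, the visit sections, Table 3a footnote n (which fixes Part C post-dose assessments at 4-5 h), Section 10.1.3.9 and the Part B Dosing Guidance letter all point to the intended timing. To lose an ECG, a site would have to leave a marked cell empty and use an unmarked one. Table 5 says the Part C post-Dose 6 PK time, 4-5 h, is the same as in Part B. This suggests, though it does not state, that the Part B time had already been chosen, in which case amending Table 2 may change little in practice. No analysis or dose decision is shown to change. These points limit the severity; they do not make the footnote correct.

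**Conclusion.** The inconsistency is real: footnote f of Protocol Tables 2 and 3a is wrong as written for two of the six dosing-day ECGs, those after Dose 1 and Dose 6. It is minor, because the correct timing can be worked out from the rest of the protocol and most sites would probably do so.

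The possible loss is one or both post-dose ECGs in an infant at a site that follows the footnote. It matters more in Part B, where ECG change is a primary safety endpoint, than in Part C, where it is not listed. The counts assume the twice-daily, 10-dose schedule shown in the tables. The number of infants affected cannot be estimated from the documents.

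**What to change.** At the next amendment, add the closing exception of Table 3b footnote j to footnote f of Protocol Tables 2 and 3a. All six dosing-day ECGs would then agree with the row and the visit sections. Send sites a one-line clarification that the Dose 1 and Dose 6 ECGs are taken at the scheduled post-dose time.

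SAP Tables 2 and 3 copy the footnote without the exception; aligning them is optional housekeeping. The cost is one clause in two protocol footnotes and a short site message, with no additional ECG, visit or analysis.
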